## **12.11. Additional Visits**

An Additional Follow-up Visit will be reported when an office/clinic visit identifies a reportable event and the device is interrogated. If possible, a device evaluation and lead measurements should be performed and the results recorded in the EDC system.

### **12.11.1. Required Data Collection**

1. Complete the Additional Follow-up form
2. Collect any adverse event information
3. Print the ‘Quick Notes’ Report

### **12.11.2. Recommended Data Collection**

1. It is recommended to conduct a device evaluation:
  - Manual pacing threshold tests
  - Sensing amplitude
  - Impedance
  - Shock impedance (RV lead only)
2. For all additional visits after an MR scan, the PG data should be reviewed. If any new episodes of polymorphic or monomorphic VT or VF that required ATP or shock therapy are present since the prior study visit:

- i. Print the ‘Arrhythmia Logbook’ and ‘Selected Episodes Report’ (counters and EGMs) using the PRM
- ii. A copy of the Selected Episode Report(s) with counters and EGMs is expected to be submitted to Boston Scientific within 5 business days using the upload tool in the EDC system

3. Perform a Save All:

- a) Save device data to a USB using the programmer “Save All” feature
- b) Label the USB with the subject ID#, Date, and “Additional Follow-up”
- c) Retain the original USB at the center, and a copy is expected to be submitted to Boston Scientific using the upload tool in the EDC system. Do not make a copy by using the programmer a second time as this will create a new USB with slightly different information.

#### **12.11.3. Additional Follow-up Visit Source Data Requirements**

Source data Requirements at Additional Follow-up Visit are described in Table 12-10.

**Table 12-10 Additional Follow-up Source Documentation Requirements**

Source Documentation Requirement	Disposition
Device Evaluation (pace threshold, sense amplitude, impedance, RV shock impedance)	
PRM ECG strips from manual threshold tests documenting LOC for all implanted leads	
Documentation of spontaneous VT/VF episode(s) by PRM strips, as applicable: 

• ‘Selected Episodes Report’ (counters and EGMs required)

• ‘Arrhythmia Logbook’

	Retain at center
Printout of ‘Quick Notes’ Report	
Adverse Events	
Save All, as applicable	Retain the original at the center and submit a copy to Boston Scientific

*Text in table that is italicized is recommended*

### 12.12. Medically Necessary MRI Visits

During the study, if a subject needs a medically necessary MR scan, BSC recommends the subject be directed to have the scan at the Study site.

Note: In case the medically necessary MR scan is performed at a non-investigational site, all efforts must be made to collect the data and adhere to the MRI Conditions of Use.

Study flow is identical to the MRI visit as described in section 12.7. Some data collection is optional for Medically Necessary MRI visit as shown in italic in Table 12-11.

For medically necessary MRI scans, all activities performed by the site Principal Investigator or a sub-investigator at the MRI visit (i.e. heart rhythm monitoring) can be performed by a trained and qualified Health Care Professional (HCP).

As for the MRI visit, it is recommended to have a programmer powered ON in Zone II near the MRI room in case the patient develops the urgent need for pacing.

#### 12.12.1. Medically Necessary MRI Visit Source Data Requirements

Source data Requirements for medically necessary MR scans are described in Table 12-11:

**Table 12-11 Medically Necessary MRI Visit Source Documentation Requirements**

Source Documentation Requirement	Disposition
Pre-MR scan: 

• Body part scanned

• Assessment of patient history of unexplained syncope

• Device Evaluation (pace threshold, sense amplitude, impedance, RV shock impedance, LV Phrenic Stimulation threshold)

• PRM ECG strips from manual threshold tests documenting LOC for all implanted leads

• Evaluation of Beeper function

• Printout of 'Quick Notes' Report

• Cardiology and Radiology MRI Conditions of Use are satisfied

	Retain at center
MR scan: 

• MRI Protection Settings Report

• Time of MR scan initiation

• Time of MR scan completion MRI

	Retain at center

 
• Heart rate in 5 ± 2 minute intervals
 
• Medications used for sedation in the MR scanner, if applicable
 
• MR Scanner manufacturer and model
 
	
When PG is programmed out of MRI Protection Mode: 
 
• Time of exiting MRI Protection Mode
 
	Retain at center
Post-MR scan: 
 
• Device Evaluation (pace threshold, sense amplitude, impedance, RV shock impedance, LV Phrenic Stimulation threshold)
 
• PRM ECG strips from manual threshold tests documenting LOC for all implanted leads
 
• Evaluation of Beeper function
 
• Document if polymorphic or monomorphic VT/VF episodes requiring therapy, are present
 
• Documentation of spontaneous VT/VF episode(s) by PRM strips, as applicable: 
 
■ 'Selected Episodes Report' (counters and EGMS required)
 
■ 'Arrhythmia Logbook'
 
 
 
• Printout of 'Quick Notes' Report
 
• Assessment of MR scan image quality
 
	Retain at center
Adverse Events	Retain at center
MR scanner DICOM dump/ report file including items such as scan sequence settings and durations as well as calculated scan metrics such as whole body average SAR. The DICOM file must contain both images and scan sequence data.	Retain the original at the center and submit a copy to Boston Scientific
Save All	Retain the original at the center and submit a copy to Boston Scientific

*Text in table that is italicized is recommended*

### 12.13. Study Completion

Subjects will be followed until completion of the Implant + 1 Year Visit. The individual

subject will finish the study when he/she completes the Implant + 1 Year Visit.

Note: Phase I is completed when all the subjects finish MRI + 1 Month Visit, and the data will be summarized to support product CFDA registration.

## **13. Statistical Considerations**

### **13.1. Primary Endpoints**

#### **13.1.1. Primary Safety Endpoint: MR Scan-Related ImageReady System Complication Free Rate**

The primary safety endpoint of the MR ICD study will be assessed for all subjects who undergo any portion of the study-required MR scan sequences. Safety will be confirmed by evaluating the MR scan related ImageReady System complication-free rate (CFR) between the MR Scan and the MRI Visit + 1 Month.

For the purpose of this endpoint, a MR scan-related ImageReady System complication will be defined as those complications that are related to the MR scan and ImageReady System. All complications that the site reports as related to the MR scan and ImageReady System will be adjudicated by an external committee for relation to the MR scan. Complications that are determined to be associated with the MR scan will be considered MR scan-related complications and count against this endpoint. Complication is defined as serious adverse event or permanent loss of device functions (i.e. pacing or defibrillation).

The performance goal of the primary safety endpoint for the ENABLE MRI study (MR scan related ImageReady System complication free rate) was 90%. There is no hypothesis testing in the MR ICD study, and it can be considered reasonable if up to 2 failed cases of primary safety endpoint event may occur. Descriptive statistics will be conducted for the endpoint events.

The data set for the primary safety endpoint will include all subjects who undergo the study-required MR scan sequences (scan sequences initiated, whether complete or not). The time window for MRI + 1 Month visit is 30±7 days post MR scan, so it will capture events within at least 23 days post scan. In this small sample size study, missing data will be excluded.

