### **13.4. General Statistical Methods**

#### **13.4.1. Control Bias**

Selection of patients will be made from the Investigator's usual patient load. All patients meeting the eligibility criteria and having signed the ICF will be eligible for enrollment in the study. An independent Clinical Events Committee (CEC) will determine the MR Scan-related ImageReady System complications. The study will be conducted in approximately 5 sites and one single site may not enroll more than 10 subjects generally.

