## **21.7. Subject Death reporting**

A subject death during the study should be reported to Boston Scientific as soon as possible and, in any event, within 24 hours of site notification. The site's EC must be notified of any deaths in accordance with that site's EC policies and procedures.

Notification of death must include a detailed narrative (death letter) that provides detailed information describing the circumstances surrounding the death. A death narrative in the local language is acceptable, if accompanied by a translation in English. The details listed below should be addressed in the death narrative, in order for BSC to understand the circumstance surrounding the death:

- Date and time of death
- Place death occurred
- Immediate cause of death
- Rhythm at the time of death, if known (include any available documentation)
- Whether the death was related to the pulse generator, lead/catheter, clinical investigation, procedure, or patient condition
- Whether or not the death was witnessed
- Device status and/or activity at the time of death (device recipients only – pacing and defibrillation, active or inactive)
- Whether the patient had worsening heart failure
- Any other circumstances surrounding the death
- Approximate time interval from the initiating event to death (temporal course) items to consider include, but are not limited to: information regarding last time subject was seen by investigator, last office visit, etc.
- Investigator or sub-investigator signature and date

Also submit the following documentation, if the patient expired in the hospital:

- A copy of the medical records for that admission (e.g., H & P, consults, test results, operative reports, and/or progress notes from the hospital chart)
- Death certificate (if available)
- Autopsy report (if applicable)
- If the patient expired outside of the hospital (e.g., home):
- A copy of the most recent clinic visit (if not already submitted to Boston Scientific)
- Death certificate (if available)

Whenever possible, the IPG should be interrogated. Investigational leads and related Boston Scientific RM system components (e.g., IPGs) should be removed intact and returned promptly to Boston Scientific RM for analysis. The Clinical Events Committee (CEC) must review information regarding subject deaths.

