### **23.2. Clinical Events Committee**

A Clinical Events Committee (CEC) will be used in this study. A CEC is an independent group of individuals with pertinent expertise, including Cardiology, which reviews and adjudicates important endpoints and relevant adverse events reported by study investigators. The CEC will review a safety event dossier, which may include copies of subject source documents provided by study sites, and adjudicate study endpoint related clinical events.. The responsibilities, qualifications, membership, and committee procedures of the CEC are outlined in the CEC charter.

For the purpose of the study primary safety endpoint, an MR scan-related ImageReady System complication will be defined as those complications that are related to the MR scan and ImageReady System. All complications that the site reports as related to the MR scan and ImageReady System will be adjudicated by an external committee for relation to the MR scan. Complications that are determined to be associated with the MR scan will be considered MR scan-related complications and count against this endpoint.

Complication is defined as serious adverse event or permanent loss of device functions (i.e. pacing or defibrillation).

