### 5.1.2 Primary safety endpoint analysis:

The primary safety endpoint of the MR ICD study will be assessed for all subjects who undergo any portion of the study-required MR scan sequences. Safety will be confirmed by evaluating the MR scan related ImageReady System complication-free rate (CFR) between the MR Scan and the MRI Visit + 1 Month. This endpoint is analyzed based on Implant population. Counts and percentages presenting 95% Clopper-Pearson confidence interval with two-sided exact binomial confidence bound at 95%.

Complications that are determined to be associated with the MR scan will be considered MR scan-related complications and count against this endpoint. Complication is defined as serious adverse event or permanent loss of device functions (pacing/defibrillation).

All the primary efficacy endpoint and safety endpoint been summarized presenting 95% Clopper-Pearson confidence interval with two-sided exact binomial confidence made for both Intent and Implant study populations. If subject’s status been categorized to either Attempt or Partial Implant, then the results been presented for both these populations as well.

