#### **5.3.4 Analysis of Adverse and Serious adverse events**

Subject-level event rates will be calculated at various time points (e.g. exact days) based on all events reported by the site regardless of whether they are ultimately adjudicated. Frequency of site reported Serious adverse events and non-serious adverse events and also Frequency of site-reported Serious adverse events and Non-serious adverse events are associated with the implant procedure up to MRI Visit+1 Month are exhibited using counts and percent with total available subjects based on safety population. The events are summarized by MedDRA system organ class and MedDRA system preferred terms with events and rates.

For calculating events and rates, need to consider ‘Events numbers’ are total episodes of each type of event among all subjects. ‘Rate of Subjects with Event’ numbers are percent of subjects who experienced one or more episodes of the event. ‘Events’ numbers for “TOTAL” are the sum of the individual event category totals. ‘Rate of Subjects with Event’ numbers for “TOTAL” is the percent of subjects who experienced an adverse event.

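### For non-fatal complications, the only stated route to primary safety adjudication is the site's own call that the event is related; no stated step lets the committee add an unflagged event

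*Combined protocol and SAP*

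**What the plan says.** Protocol 13.1.1 defines a complication as a serious adverse event or a permanent loss of device function. It counts those related to the MR scan and the ImageReady System, and gives this rule for reaching the committee: "All complications that the site reports as related to the MR scan and ImageReady System will be adjudicated by an external committee". The committee's question, as the same sentence frames it, is only whether the event relates to the scan. Section 23.2 repeats the rule and ties it explicitly to this endpoint.

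Elsewhere the committee's role is described more broadly:

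- Protocol 13.4.1 and SAP 4.2, both on bias: "An independent Clinical Events Committee (CEC) will determine the MR Scan-related ImageReady System complications".
- Protocol 23.2, general remit: the CEC "reviews and adjudicates important endpoints and relevant adverse events reported by study investigators". Its procedures are left to a charter.
- Protocol 21.7: "The Clinical Events Committee (CEC) must review information regarding subject deaths".
- SAP 5.1.2: "Complications that are determined to be associated with the MR scan will be considered MR scan-related complications and count against this endpoint". It does not say which events are reviewed.
- SAP 5.3.4: adverse event rates are "based on all events reported by the site regardless of whether they are ultimately adjudicated".

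Protocol 13.1.1 and SAP 3.1 treat up to 2 failed cases as acceptable.

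**The concern.** Independent adjudication protects an endpoint when the committee sees events regardless of how the site attributed them. Here the site's attribution comes first. The study has one arm and every subject in the safety set has been scanned, so the site makes that call knowing the exposure.

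As written, the committee works in one direction: it can confirm or remove a flagged event, but nothing states that it can add one. It is asked only about relation to the scan, so relation to the system rests on the site's report. Any true event that the site does not flag raises the complication-free rate. The Phase I summary, which contains this result, is meant to support product registration.

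There is a further consequence. Protocol 13.1.2 to 13.1.6 drop subjects with a lead-related complication between the MRI Visit and the MRI + 1 Month Visit from all five effectiveness data sets. If the site judged such a non-fatal complication unrelated to the scan, then under the stated rules it would be missing from the safety count and the subject from every effectiveness count.

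**Working it through.** **Step 1: is there another stated route for a non-fatal event?**

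| Place | What it provides | Referral of an unflagged non-fatal event? |
|---|---|---|
| Protocol 13.1.1, 23.2 (endpoint rule) | Site-flagged complications go to the committee | No |
| Protocol 23.2 (general remit) | Important endpoints and relevant events; relevance is not defined | No trigger stated |
| Protocol 13.4.1, SAP 4.2 | CEC determines the complications | Does not say how events arrive |
| Protocol 21.7 | CEC reviews deaths, with no condition on attribution | Deaths only |
| Protocol 18.2 | Report to the Ethics Committee includes causality by investigator and sponsor | No onward step to the CEC |
| Protocol 21.3, Table 21-2 | Investigator grades relation to device or procedure | No |
| Protocol 23.1 | Sponsor and CRO safety teams review and classify events | No onward step to the CEC |
| SAP 5.1.2 | Counts events determined to be scan-associated | No |
| SAP 5.3.4 | Tabulates all site-reported events | Outside the endpoint |

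Deaths apart, the site's report is the only stated trigger. Table 21-2 has no criteria specific to the MR scan, and neither document says which of its grades counts as related for this purpose.

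**Step 2: what one event does to the result.** The plan gives no figure for adjudication coverage, so there is none to reproduce. Inputs are the acceptance count of 2 (13.1.1), 20 planned subjects, and 8 + 8 = 16 as the minimum completing all sequences (13.3). The interval is the SAP's two-sided 95% Clopper-Pearson.

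| n | Failures | Complication-free | 95% interval |
|---|---|---|---|
| 20 | 2 | 18/20 = 90% | 68.3% to 98.8% |
| 20 | 3 | 17/20 = 85% | 62.1% to 96.8% |
| 16 | 2 | 14/16 = 87.5% | 61.7% to 98.4% |
| 16 | 3 | 13/16 = 81.25% | 54.4% to 96.0% |

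At n = 20, 2 failures equal the 90% performance goal that 13.1.1 cites from ENABLE MRI.

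**Step 3: how likely the rule is to matter.** Let p be the true proportion of subjects with a qualifying complication and s the chance that the site flags it, independently across subjects. The documents give neither, so both are assumptions. Counted failures X follow Binomial(20, p·s), and the rule is met with probability

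P(X ≤ 2) = Σ (k = 0 to 2) C(20, k) (ps)^k (1 − ps)^(20−k).

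For p = 10%:

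- s = 1: 0.1216 + 0.2702 + 0.2852 = 0.677.
- s = 0.7, so ps = 0.07: 0.2342 + 0.3526 + 0.2521 = 0.839.

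| True rate p | s = 1 | s = 0.9 | s = 0.7 |
|---|---|---|---|
| 1% | 0.999 | 0.999 | above 0.999 |
| 5% | 0.925 | 0.941 | 0.969 |
| 10% | 0.677 | 0.733 | 0.839 |
| 15% | 0.405 | 0.481 | 0.648 |

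The smallest gain at p of 10% to 15% is 0.733 − 0.677 = 0.056, and the largest is 0.648 − 0.405 = 0.243. At p = 5% the gains are 0.941 − 0.925 = 0.016 and 0.969 − 0.925 = 0.044. At p = 1% the gain is below 0.001.

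**The case against.** The strongest reply is that the rule sets a minimum. Saying that all site-flagged complications go to the committee does not bar others, and 23.2 gives a general remit not conditioned on attribution. The bias sections assign the CEC the whole construct, scan and system together, and within the SAP section 4.2 answers who determines the events counted in 5.1.2. The charter or the safety plan may hold a wider trigger. This stands in part: the gap is shown in the protocol and SAP, not in practice. It does not remove the gap, because the general remit leaves relevance undefined, and the endpoint-specific rule in the same section is the narrow one.

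Second, there are other safeguards. Sponsor physicians classify events, causality is also assessed by the sponsor, Table 21-2 defaults to possibly related when relatedness cannot be assessed, and the scheduled device tests measure pacing function. These make under-flagging less likely, but none states that an unflagged event goes on to the CEC.

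Third, the effect needs frequent events. The registry described in the protocol's introduction reported no deaths, lead failures, losses of capture or ventricular arrhythmias during MRI in 1,500 non-thoracic scans. If p is near 1%, the chance of 3 or more true failures in 20 is about 0.1%. This is a fair limit on the size. The registry scans were non-thoracic, however, whereas this protocol centres its RF-intensive sequences on the thoracic spine.

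Finally, there is no hypothesis test, and unflagged complications would still appear in the adverse event tables. That is true, but they would sit outside the primary count by which safety is judged.

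**Conclusion.** The concern holds. For non-fatal complications, the plan states one route into primary safety adjudication, the site's own report of relatedness, and no step by which the committee could add an event. The bias control claimed in protocol 13.4.1 and SAP 4.2 is therefore not fully delivered by the written procedure, and any resulting error favours the device.

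The practical size depends on two quantities that the documents do not give. With 70% to 90% flagging, the chance of meeting the count at n = 20 rises by about 6 to 24 percentage points at true rates of 10% to 15%, by about 2 to 4 points at 5%, and negligibly at 1%. That the sites are unblinded is inferred from the single-arm design. The conclusion is about the protocol and SAP; the charter was not available. It is a change that should be made, and confidence is medium.

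**What to change.** In protocol 13.1.1 and 23.2 and SAP 5.1.2, require that every complication (serious adverse event or permanent loss of device function) with onset between the start of the MR scan and the MRI + 1 Month Visit in a scanned subject goes to the existing CEC, whatever relatedness the site assigns. Have the committee judge both relation to the MR scan and relation to the ImageReady System, and count the events it finds related to both. The endpoint definition is unchanged. In SAP 5.1.2, name the CEC as the body that decides. If the charter already requires this, state it in 13.1.1 and 23.2.

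The cost is an amendment to the wording, aligned with the charter, with Ethics Committee approval where protocol section 15 requires it, and a few more dossiers: about 20 subjects, about one month each. No new visit, procedure or assessor is needed.

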### **13.1.2. Primary Effectiveness Endpoint 1: Pre-MR Scan vs. 1 Month Post-MR Scan RV shocking impedance**

The normal RV shocking impedance measured by the system should be  $\leq 200$  Ohm, with  $>200$  Ohm considered abnormal. The primary effectiveness endpoint 1 is defined as that the average RV shocking impedance is  $>200$  Ohm 1 month post scan, while it is  $\leq 200$  Ohm before scan.

There is no hypothesis testing in the MR ICD study, and it can be considered reasonable if up to 2 failed cases of primary effectiveness endpoint 1 occur.

The data set for the primary effectiveness endpoint 1 will only include subjects who undergo the study-required MR scan and complete all the sequences, and will not include subjects that meet any of the following exclusions:

- Has a medically necessary scan between implant and the MRI + 1 Month Visit
- Fails to meet labeled MRI Conditions of Use
- Experiences a lead-related complication between MRI Visit and the MRI + 1 Month Visit

The time window for MRI + 1 Month visit is  $30 \pm 7$  days post MR scan, so it will capture events within at least 23 days post scan. In this small sample size study, missing data will be excluded.

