### **8.2. Primary Effectiveness Endpoints**

1. Abnormal increase in RV shocking impedance from the pre-MR scan to the 1 Month post-MR scan
2. Increase in RV pacing threshold (at 0.5ms) from the pre-MR scan to the 1 Month post-MR scan
3. Decrease in RV sensed amplitude from the pre-MR scan to the 1 Month post-MR scan
4. Increase in LV pacing threshold (at 0.5ms) from the pre-MR scan to the 1 Month post-MR scan
5. Decrease in LV sensed amplitude from the pre-MR scan to the 1 Month post- MR scan

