**Figure 9-1 MR ICD study Design**

## 9.2. Justification for the Study Design

BSC is conducting a global multi-center study, ENABLE MRI (NCT02652481), on MR conditional systems including DYNAGEN and INOGEN. The study will enroll 500 subjects, to confirm the safety and effectiveness of the ImageReady™ MR Conditional Defibrillation System when used in the 1.5T MRI environment under the labeled Conditions of Use. CFDA requires certain clinical trial in China to support the approval of ImageReady™ MR conditional defibrillation system.

The MR ICD study referenced ENABLE MRI. The major difference is that ENABLE MRI will collect 25 episodes of VT/VF events post MR scan, while the small sample size MR ICD study would use shocking impedance measurement to evaluate the integrity of the shocking circuit. The MR ICD study will also assess any VT/VF event post MR scan.

The MR ICD study is composed of two phases. Phase I is completed when all the subjects finish MRI + 1 Month Visit, and the data will be summarized to support product CFDA registration. All subjects will be followed-up till 1 year post implantation.

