### **13.2. Ancillary Assessments**

The ancillary endpoints are not formal endpoints.

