### **3.3 Ancillary Assessments**

*The ancillary endpoints are not formal endpoints*

- Changes in RV and LV impedances pre-MR scan versus 1 Month post-MR scan (MRI Visit and MRI + 1 Month Visit) assessed for RV and LV Impedances
- Changes in RA lead measurements including pacing thresholds, sensed amplitudes and impedances, between pre- and 1 Month post-MR scan measurements assessed for RA lead measurements
- The detection time (first elapsed time), therapy given and conversion result, shocking impedance (if applicable) assessed for post MR scan VT/VF episodes. For a VT/VF episode, there might be no therapy, ATP or Shock therapy. Only shock therapy will have a shocking impedance, while shock for VT/VF might be very few in this small sample study. Data collected from Arrhythmia Logbook Report used for Assessment of VT/VF post MR scan and only VT/VF episodes from Arrhythmia log book considered for analysis. Detection time, Therapy given are summarized based on subject total episodes from visit and shocking impedance summarized based on subjects.
- The following information will be summarized for both study-related MR scans and medically necessary MR scans:
  - Duration of the PG in the MRI Protection Mode
  - Time from the start of the MRI Protection Mode to the start of the MR scan
  - Time from the end of the MR scan to exiting the MRI Protection Mode
- MR image quality scores will be presented in study report for assessment of Image Artifacts for non-medically necessary MR scans

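### Endpoint 1 counts only a rise above 200 Ohm, so an unrecognised fall in RV shock impedance scores as a success on the study's main measure of shocking-circuit integrity

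*Combined protocol and SAP*

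**What the plan says.** Protocol section 8.2 lists endpoint 1 as "Abnormal increase in RV shocking impedance from the pre-MR scan to the 1 Month post-MR scan". Section 13.1.2 gives the normal range ("The normal RV shocking impedance measured by the system should be" no more than 200 Ohm) and then the event: "The primary effectiveness endpoint 1 is defined as that the average RV shocking impedance is" above 200 Ohm one month after the scan, having been 200 Ohm or less before it. Up to 2 failed cases are considered reasonable. SAP 3.2 i carries the same definition. SAP 5.1.1 scores each subject as success or failure and reports the success proportion with a 95% Clopper-Pearson interval.

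Sections 8.3 and 9.2 explain why the endpoint exists. ENABLE MRI collects 25 VT/VF episodes after the scan, whereas this study "would use shocking impedance measurement to evaluate the integrity of the shocking circuit". Section 9.2 adds: "The MR ICD study will also assess any VT/VF event post MR scan". That assessment is ancillary, and section 13.2 says of such items: "The ancillary endpoints are not formal endpoints".

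**The concern.** The stated purpose is the integrity of the shocking circuit, which can be lost in two directions. An open circuit raises the measured impedance; a short circuit or insulation failure lowers it. That link is engineering reasoning and is not stated in the documents, although Table 20-1 lists lead insulation breakage and inability to defibrillate among the potential adverse events. The rule responds to one direction only, and neither document says why only an increase counts.

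At stake is what a clean endpoint 1 result means. Phase I data are to support registration, and this is the only primary effectiveness endpoint directed at the shocking circuit. With zero failures, a reader could not tell from the endpoint whether impedance was stable or had fallen.

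**Working it through.** The 200 Ohm limit is set, not derived, so there is no figure of the plan's to reproduce beyond the sample size: 10 − 2 = 8 per group, 16 in total, out of 20 enrolled.

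**Step 1. The rule.** From section 13.1.2 and SAP 3.2 i: event = (1-month average > 200 Ohm) and (pre-scan average ≤ 200 Ohm).

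**Step 2. Apply it.** The documents give no typical baseline. Taking 60 Ohm as an illustration:

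| 1-month average (Ohm) | Change from 60 Ohm | Scored |
|---|---|---|
| 0.1 | −99.8% | no event |
| 5 | −91.7% | no event |
| 20 | −66.7% | no event |
| 60 | 0% | no event |
| 120 | +100% | no event |
| 200 | +233% | no event |
| 200.1 | +234% | event |
| 250 | +317% | event |

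For an assumed baseline of 40 to 80 Ohm, an event needs a rise of more than 200 − 80 = 120 Ohm (150% of 80) to 200 − 40 = 160 Ohm (400% of 40). No fall is ever an event, whatever baseline is assumed.

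**Step 3. The extreme case.** If all analysed subjects fell to near zero and none was recognised as a lead-related complication, failures = 0. With n successes out of n, the Clopper-Pearson lower limit is 0.025^(1/n): 0.025^(1/16) = 0.794 and 0.025^(1/20) = 0.832. The report would show 100% success with intervals of 79.4% to 100% or 83.2% to 100%.

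**Step 4. Effect on the acceptance rule.** Let q be the true rate of low-side failures (assumed values) and suppose there are no others. Under a two-sided rule, the chance of meeting the up-to-2 criterion is P(X ≤ 2) with X ~ Binomial(n, q):

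| q | n = 16 | n = 20 |
|---|---|---|
| 5% | 0.957 | 0.925 |
| 10% | 0.789 | 0.677 |
| 20% | 0.352 | 0.206 |
| 30% | 0.099 | 0.035 |

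Under the current rule the chance is 1.0 at every q.

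**Step 5. What else could catch a fall.**

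- *Safety endpoint (13.1.1).* Permanent loss of defibrillation is a complication. It counts only if the site reports it as related to the scan and the system and the committee confirms the relation to the scan.
- *Lead-related complication (13.1.2).* A recognised one between the MRI Visit and MRI + 1 Month removes the subject from endpoint 1. It is neither a success nor a failure there.
- *VT/VF episodes (13.2.3, SAP 3.3).* These are ancillary. The SAP itself warns: "Only shock therapy will have a shocking impedance, while shock for VT/VF might be very few in this small sample study".
- *Ancillary impedance change (13.2.1).* This names RV and LV impedances. Table 12-3 treats shock impedance as a separate test, and SAP 5.1.3 speaks of pacing impedance, so a summary of change in shock impedance is not clearly planned.
- *Listing (SAP 5.3.3).* Shock impedance is listed by subject and visit, with no criterion for a low value.

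**The case against.** The strongest reply is that the study as a whole is not blind to a low-impedance failure. A reader might infer from the endpoint 1 rule that lost defibrillation through low impedance can never produce a failure. The documents do not support that: section 13.1.1 makes permanent loss of defibrillation a complication that can count against the primary safety endpoint, and device deficiencies must be reported under section 21. Nor is every short circuit scored as intact, because a recognised lead-related complication leaves the data set. Nor is VT/VF evidence dropped altogether, since therapy and conversion result are still described.

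It can also be said that the plan promises no conclusion of an intact circuit. There is no hypothesis test, results are descriptive, and with 16 to 20 subjects and three sets of readings at each key evaluation a near-zero value would be visible in the listing. Finally, the documents do not say that MRI lowers shock impedance. Section 4 names lead-tip heating with loss of capture and arrhythmia from unexpected pacing. Section 20.3 lists loss of defibrillation therapy only for scans outside the Conditions of Use, and those subjects are excluded from endpoint 1.

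These points limit the concern but do not remove it. The safety route depends on someone noticing, reporting and attributing the problem, and a low reading that the protocol classes as normal gives little prompt to do so. The exclusion avoids a false success without recording a failure. Shocks are expected to be very few, and a visible value with no criterion is left to judgement after the data are seen.

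**Conclusion.** The concern holds for endpoint 1: as defined in both documents, it cannot register a fall in RV shock impedance, and an unrecognised fall counts as a success. This matters because sections 8.3 and 9.2 rest the study's main evidence of shocking-circuit integrity on this measurement. The other provisions give partial, mostly non-formal cover.

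The definition applies to every analysed subject, but a result changes only if someone's impedance falls, and the documents give no basis for saying how likely that is. The 40 to 80 Ohm and 60 Ohm baselines and the failure rates in step 4 are illustrative; the finding rests on the wording of the rule. The step 3 case shows what the rule allows and does not predict what will happen.

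**What to change.** 1. Make endpoint 1 two-sided in protocol 13.1.2 and SAP 3.2 i. An event is a MRI + 1 Month average outside the device's own out-of-range limits in either direction, when the pre-scan average was within them.
2. Have the sponsor state and justify the low limit from device labelling. The documents give none, and nothing in them shows that the MRI Technical Guide contains one. Section 20.3.1 mentions a lead-impedance out-of-range alert but not its limits.
3. Report the within-subject change in shock impedance from pre-scan to MRI + 1 Month beside the event count.
4. Rename item 1 of section 8.2, and the matching synopsis entry, to *Abnormal change in RV shocking impedance*.

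No new measurement is needed. Three sets of readings are already taken before the scan and at MRI + 1 Month (12.7.1, 12.8.1), in the same configuration (Table 12-3). Endpoints 3 and 5 already combine an absolute limit with a relative change.

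The cost is a protocol and SAP amendment, with Ethics Committee approval under section 15 where the change bears on scientific integrity, and a failure count that may rise. It could fall only in the unlikely case of a subject below the low limit before the scan who later exceeds 200 Ohm. If analyses have already been run, SAP 5.4 requires the change and its reason to appear in the clinical study report.
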